# 6.3. Measures to Minimize Bias: Randomization and Blinding

All participants will be centrally assigned to randomized study intervention using an IWRS. Participants will be randomized in a 1:1:1 ratio to tirzepatide 5 mg QW:tirzepatide 10 mg QW:placebo QW.

Participant stratification factors are:

- age (< 14 years of age, >14 years of age), and
- baseline antihyperglycemic medication use of
  - o metformin only, or
  - o basal insulin only, or
  - metformin and basal insulin.

# **Double-blind period**

Investigators, site staff, clinical monitors, and participants will remain blinded to the treatment assignments until the double-blind period of the study is complete.

Emergency unblinding for AEs may be performed through the IWRS, which may supplement or take the place of emergency codes generated by a computer drug-labeling system. This option may be used ONLY if the participant's well-being requires knowledge of the participant's treatment assignment. All actions resulting in an unblinding event are recorded and reported by the IWRS.

In case of an emergency, the investigator has the sole responsibility for determining if unblinding of a participants' treatment assignment is warranted for medical management of the event. Participant safety must always be the first consideration in making such a determination. If the investigator decides that unblinding is warranted, it is the responsibility of the investigator to promptly document the decision and rationale and notify Lilly as soon as possible.

If an investigator, site personnel performing assessments, or participant is unblinded during the double-blind period, the participant must be discontinued from the study. In cases where there are ethical reasons to have the participant remain in the study, the investigator must obtain specific approval from a sponsor medical monitor for the participant to continue in the study.

# Open-label period

During this part, study intervention will be assigned using an IWRS.

# **6.4.** Study Intervention Compliance

Study intervention administration data will be recorded by the participant or parent or guardian throughout the study.

The investigator will assess study intervention compliance at each visit by reviewing

- participant's recorded administration data
- adherence to the visit schedule
- completion of study diaries, and
- any other parameters the investigator considers necessary.

The participant and parent or guardian will be instructed to return any unused study intervention and/or empty cartons at the next visit to the study site for the purpose of performing drug accountability.

[figure not shown]
Participants considered poorly compliant with their medication and/or the study procedures will receive additional training and instruction, as required, and will be reminded of the importance of complying with the protocol.

# 6.5. Dose Modification

# **6.5.1.** Tirzepatide Dose Escalation

The dose escalation scheme consists of a starting dose of 2.5 mg QW accompanied by a dose escalation of 2.5 mg increments every 4 weeks until the desired dose level is reached and maintained for the duration of the study.

This figure illustrates the tirzepatide dose escalation regimen.

# 6.5.2. Management of Increased Hypoglycemia Risk What the participant should do if they experience a hypoglycemic event

Study participant and parent or guardian will be instructed on recognizing symptoms of hypoglycemia and how to treat it. If a hypoglycemic event requires treatment assistance, then the participant or parent or guardian should call the investigative site as soon as it is safe to do so.

If safe to do so during the symptoms of hypoglycemia, the participant or parent or guardian must record in the study e-diary

- the blood glucose (BG) level measured prior to administration of treatment, if taken
- associated symptoms, and
- treatment administered.

# What the investigator should do if the participant experiences a hypoglycemic event

If a participant experiences a hypoglycemic event the investigator should

- use definitions and criteria provided in Section 8.3.3.1 to diagnose hypoglycemia,
- properly categorize the suspected or confirmed event,
- assess the effect and timing of the intervention(s),
- evaluate the frequency of the event(s),
- establish the role of dietary changes in the development of the event,
- establish the role of physical exercise, or any other contributing factor, in the development of the event, and
- provide participant additional education, if deemed appropriate.

Investigators should pay close attention as to whether the basal insulin dose needs to be reduced in participants on basal insulin, especially those who are in good glycemic control (HbA1c <7.0%).

Investigators are responsible for their participant's management and well-being. Therefore, it is their responsibility to implement these generally recommended measures, or to modify them, taking into account clinical and other relevant criteria.

#### Management of antihyperglycemic medications to reduce the risk of hypoglycemia

For participants using basal insulin who experienced hypoglycemia without an obvious cause, such as dietary or physical activity changes, the daily dose of basal insulin should be adjusted first per the clinical judgment of the investigator.

This table shows a suggested scheme for adjusting basal insulin in response to hypoglycemia and/or to reduce the risk of hypoglycemia.

If, within one week, a participant has 2 FBG results of	Then
≤50 mg/dL (<2.8 mmol/L)	Decrease the basal insulin by 8 units
>51-70 mg/dL (>2.8-3.9 mmol/L)	Decrease the basal insulin by 6 units
>70-80 mg/dL (>3.9-4.4 mmol/L)	Decrease the basal insulin by 4 units
>80 mg/dL (>4.4 mmol/L)	No adjustment needed

Abbreviation: FPG = fasting plasma glucose

In case of repeated hypoglycemic events with a low basal insulin dose, that is, less than 10 units/day, and despite basal insulin dose decreases per the titration algorithm, administration of daily basal insulin may be temporarily or permanently discontinued.

If the hypoglycemia persists despite discontinuing basal insulin and the participant takes metformin, the metformin dose may be reduced or discontinued.

# 6.5.3. Tirzepatide Dose Modifications

Dose modification for tirzepatide is not permitted.

# 6.5.4. Management of Gastrointestinal Symptoms

During the double-blind dose escalation period, every effort must be made by the investigator to maintain participants on the dose assigned by IWRS.

This table describes steps the investigator should follow to mitigate GI symptoms and manage participants with intolerable GI AEs during the escalation period.

STEP 1	Advise participants to eat smaller meals, for example, splitting 3 daily meals into 4 or more smaller meals, and to stop eating when they feel full.
STEP 2	Continue STEP 1 +  Prescribe symptomatic medication, for example, anti-emetic or anti-diarrheal medication, per local country availability and individual participant needs. Use of symptomatic medication should be captured as concomitant medication in the eCRF.
STEP 3	Continue STEP 1 + STEP 2 +  Temporarily interrupt tirzepatide; omit 1 dose, the participant will take 3 of 4 doses at that dose level. After the interruption, the investigator should restart the dose or escalate the dose as required, with the participant taking medication to alleviate their GI symptoms. The data related to temporary interruption of study treatment should be documented in source documents.
STEP 4	If intolerable GI symptoms or events persist despite the above measures, the investigator may decide to discontinue study intervention permanently.  Participants who stop study intervention permanently will intensify insulin treatment and/or receive another glucose-lowering intervention (Section 7.1) and will continue participating in the study according to the protocol to collect all planned efficacy and safety measurements. The new glucose-lowering intervention will be recorded on the eCRF for collecting anti-hyperglycemic medications.

Note: De-escalation of study intervention will not be allowed.

Abbreviations: eCRF = electronic case report form; GI = gastrointestinal.

# 6.6. Continued Access to Study Intervention after the End of the Study

Study intervention, tirzepatide, will not be made available to participants after the conclusion of the study. Participants may continue treatment with metformin available locally and/or basal insulin at investigator discretion.

#### 6.7. Treatment of Overdose

During this study, any dose of tirzepatide/placebo greater than the assigned dose within 72 h will be considered an overdose.

In the event of an overdose, the investigator must:

- 1. Contact the medical monitor immediately
- 2. Evaluate the participant to determine, in consultation with the medical monitor, whether study intervention should be interrupted
- 3. Closely monitor the participant for any AE/SAE and laboratory abnormalities
- 4. Ensure appropriate supportive treatment is initiated according to the participant's condition and symptoms

Decisions regarding dose interruptions or modifications will be made by the investigator in consultation with the medical monitor based on the clinical evaluation of the participant.

In the event of overdose, refer to the IB for tirzepatide.

# **6.8.** Concomitant Therapy

Any medication, including over-the-counter drugs, such as paracetamol or aspirin, or vaccine that the participant is receiving at the time of enrollment or receives during the study must be documented in the concomitant medications CRF. All non-diabetes concomitant therapies that are part of routine medical care that the participant requires are allowed and can be used during the study, except prescription and over-the-counter weight loss medications.

High dose inhaled or oral steroids should be used only as medically necessary.

Psychiatric medication should remain stable.

Participant or parent or guardian must consult with the investigator or a designated site staff member when they are prescribed any new medications during the study. This may not be possible when initiated for treatment of medical emergencies, in which case, the participant or parent or guardian will inform the investigator or a designated site staff member as soon as possible.

Among participants screened but not randomized, non-study medications will not be reported to Lilly unless an SAE or AE occurs that the investigator believes may have been caused by a study procedure.

# **6.8.1.** Rescue Therapy

In any situation that, in the investigator's opinion, may require an intervention that is not consistent with the requirements provided in this section, he or she must also consult the Lilly medical monitor before such intervention is implemented, except when an immediate adjustment of the treatment regimen is medically required.

Insulin therapy and metformin can be used as rescue therapy.

Rescue treatment with GLP-1 RAs or DPP-4 inhibitors are not allowed.

#### **Definition of rescue therapy**

These definitions assume that a participant has not previously received rescue therapy.

Rescue therapy is defined as any of the following changes in glucose-lowering regimen in response to persistent hyperglycemia:

- A participant treated with metformin + study intervention at baseline receives an increased dose of ≥500 mg metformin and/or insulin at any dose for more than 2 weeks
- A participant treated with metformin + basal insulin + study intervention at baseline receives an increased dose of ≥500 mg metformin and/or any increased dose of >15% basal insulin and/or adding another type of insulin at any dose for more than 2 weeks, or
- A participant treated with basal insulin + study intervention at baseline receives treatment with any increased dose of >15% basal insulin and/or adding another type of insulin at any dose for more than 2 weeks.

If a participant is experiencing severe, persistent hyperglycemia as outlined in section 8.3.3.2, the participant should be considered for rescue. If they are rescued, they will continue in the study and will continue to take study intervention unless the investigator determines that they should not.

#### **6.8.2.** Allowed Acute Diabetes Therapies

Antihyperglycemic medications other than study interventions are ONLY allowed during these circumstances

- for participants who require permanent discontinuation of study intervention but remain in the study
- for rescue therapy after randomization due to severe, persistent hyperglycemia, or
- during the safety follow-up period.

Short-term insulin use for up to 14 days is allowed for certain clinical situations (for example, elective surgery, during hospitalization, hyperosmolar states) and must be differentiated from insulin use as rescue therapy when reported in the electronic case report form (eCRF).

#### 6.8.3. Allowed Chronic Diabetes Therapies

The only allowed concomitant chronic diabetes therapies are metformin and basal insulin.

#### Use of metformin

After randomization, discontinuation of metformin or change in dosage and formulation is not permitted except in these situations:

- In the event of a hypoglycemic episode(s) (clinical symptoms of hypoglycemia and/or fasting blood glucose [FBG]-confirmed symptomatic hypoglycemia of glucose concentration <3.0 mmol/L [54 mg/dL]), participants should first reduce or discontinue basal insulin (if applicable) and then may reduce or discontinue the dose of metformin only after discontinuing basal insulin (if applicable).
- In certain situations that require short-term discontinuation in line with the product(s) labeling for each respective country, for example, for severe dehydration, elective surgery, or need for radiologic examination involving intravenous (IV) iodinated contrast dye. Once the situation that led to temporary discontinuation is resolved, treatment should be restarted at investigator discretion.
- If a participant develops contraindications to metformin such that the use of the drug is contraindicated according to the country-specific label.
- If a participant meets the criteria for severe, persistent hyperglycemia (Section 8.3.3.2) or discontinues study intervention, then the metformin dose may be increased according to country-specific label.

A participant will be considered noncompliant with the protocol (protocol deviation) if he or she changes the dose or discontinues metformin for reasons other than those described here. Dose reduction/discontinuation of metformin during the study must be properly documented and recorded on the appropriate eCRF.

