# Hypoglycemia

Participants with baseline HbA1c <8% and on basal insulin will be instructed to reduce the dose of basal insulin by 20% upon randomization to reduce the risk of hypoglycemia. If a hypoglycemic event occurs, insulin therapy and metformin doses may be further reduced or stopped as detailed in Section 6.5.2.

For complete details regarding the management of hypoglycemia risk, see Section 6.5.2.

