# 4.2. Scientific Rationale for Study Design

This is a superiority study, the main objective of which is to compare the effects of tirzepatide 5 mg and tirzepatide 10 mg QW (pooled), with metformin or basal insulin, or both to those on placebo for glycemic control (defined as change from baseline in HbA1c) in pediatric and adolescent population with T2DM over a 30-week period, followed by a 22-week open-label extension.

The efficacy measure, HbA1c, was chosen as the primary objective because it is an accepted endpoint in glycemic studies in pediatric and adolescent participants with T2DM.

The use of placebo for 30 weeks during the double-blind portion of the study is considered appropriate, as Phase 3 studies with tirzepatide have not been conducted to date in the pediatric and adolescent population. Thus, a placebo comparator is necessary to understand tirzepatide's true safety and efficacy. To protect the safety of the participants enrolled across all arms of this study, the double-blind period is relatively short, there are clear rescue criteria for participants with severe, persistent hyperglycemia (see Section 8.3.3.2) and participants are allowed to decrease basal insulin and/ or metformin as needed if hypoglycemia occurs (for the definition of hypoglycemia, see Section 8.3.3.1).

The doses of tirzepatide for this study were based on efficacy, safety and PK/PD data from two placebo-controlled studies in adults with T2DM, SURPASS-1 (GPGK), monotherapy study versus placebo and SURPASS-5 (GPGI), add-on to basal insulin vs placebo.

To mitigate the occurrence of GI AEs and permit time for the development of tolerance to GI effects, a dose escalation scheme will be used that starts at a low dose of 2.5 mg QW for 4 weeks and then escalates 2.5 mg increments every 4 weeks (Section 6.5.1). Therefore, it will take 4 weeks of dosing to reach a maintenance dose of 5 mg and 12 weeks to reach a maintenance dose of 10 mg.

The background therapies of diet and exercise, with metformin or basal insulin or both, are considered appropriate, as these are approved treatments for pediatric and adolescent participants with T2DM in the US, EU, and many countries around the world.

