In adults, tirzepatide has been shown to be effective in lowering HbA1c with consistent safety in the monotherapy setting (diet and exercise only) and when added to metformin and other oral anti-diabetes agents and/or basal insulin. The decision not to maximize the doses of metformin and basal insulin was considered appropriate, as metformin at a dose of  $\geq 1000$  mg/day is considered an effective dose in pediatric participants. For participants using basal insulin, up-titration of insulin during the double-blind period would reduce the study's ability to perceive a difference between the placebo and tirzepatide treatment arms and therefore is not allowed beyond  $\pm$  15% of the baseline dose (see Section 6.8.1). Temporary increases in insulin dose are allowed during the study and appropriate rescue methods exist in the protocol to ensure that participants do not continue in the double-blind portion of the study with poor glycemic control. Participants may decrease doses of background diabetes medications at any time if hypoglycemia is noted.

According to the visit schedule, participants will be seen by physicians in the clinic during tirzepatide dose escalation approximately every month until maintenance dose is achieved, and with telephone visits approximately every month in between the clinic visits. This is considered appropriate, as pediatric and adolescent participants with T2DM are usually seen in the clinic every 3 months.

To optimize statistical power to detect a meaningful treatment difference, there will be treatment group comparisons at the 30-week primary endpoint based on the pooled tirzepatide arms compared to placebo.

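### Protocol 6.8.3 makes a metformin cut for a symptom-free glucose below 54 mg/dL a deviation, although 6.5.2 (once basal insulin is stopped) and the rationale in 4.2 allow it

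*Protocol*

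**What the plan says.** Section 6.8.3 bars any change to metformin after randomization unless it falls under one of four listed situations. The first is a hypoglycemic episode, defined in a parenthesis as "clinical symptoms of hypoglycemia and/or fasting blood glucose [FBG]-confirmed symptomatic hypoglycemia of glucose concentration <3.0 mmol/L [54 mg/dL". Basal insulin, if used, must be stopped first. The others are short-term interruption in line with the label, a contraindication, and a dose increase for severe persistent hyperglycemia or after study drug is stopped. The section then adds: "A participant will be considered noncompliant with the protocol (protocol deviation) if he or she changes the dose or discontinues metformin for reasons other than" the listed ones.

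Other sections set a wider condition:

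- Section 4.2 says that "participants are allowed to decrease basal insulin and/ or metformin as needed if hypoglycemia occurs (for the definition of hypoglycemia, see Section 8.3.3.1". Later it adds: "Participants may decrease doses of background diabetes medications at any time if hypoglycemia is noted".
- Section 6.5.2 tells the investigator to "use definitions and criteria provided in Section 8.3.3.1 to diagnose hypoglycemia". On metformin it says: "If the hypoglycemia persists despite discontinuing basal insulin and the participant takes metformin, the metformin dose may be reduced or discontinued".
- Section 2.3.1, under Hypoglycemia, points to the same place: "If a hypoglycemic event occurs, insulin therapy and metformin doses may be further reduced or stopped as detailed in Section 6.5.2".
- Section 8.3.3.1 counts as an episode either symptoms or a glucose below 70 mg/dL, with symptom-free values included. For Level 2, below 54 mg/dL, it says that the threshold matters clinically whether or not symptoms are present.

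**The concern.** The hypoglycemia exception in 6.8.3 is narrower than the definition that sites are told to use elsewhere, and the two differ on a safety step in children and adolescents. Participants check fasting glucose three times a week (Section 4.1.1), so a low value without symptoms can come to light. If it does, and basal insulin is not in use or has already been stopped, metformin is the next background drug to lower. A site that works from 6.5.2 or 4.2 may lower it; a site that works from 6.8.3 may not, unless it accepts a deviation. At stake are consistent handling of such readings across sites and a deviation log that does not penalize a step allowed elsewhere in the protocol.

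**Working it through.** No arithmetic applies. The check is a comparison of texts.

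**Step 1: what 6.8.3 requires.** The first limb is symptoms. The second is a fasting reading below 54 mg/dL that confirms hypoglycemia described as symptomatic. Anyone who meets the second limb has already met the first, so the glucose figure admits nobody.

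**Step 2: whether the list is closed.** It is. Changes outside the list are barred, and the closing sentence makes them deviations. None of the other three situations fits a low glucose reading as such.

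**Step 3: test cases.** Take a participant on metformin who has stopped basal insulin and whose episodes continue.

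| Episode | Counts under 8.3.3.1 | Metformin cut under 6.5.2 and 4.2 | Metformin cut under 6.8.3 |
|---|---|---|---|
| Symptoms, no reading | Yes | Allowed | Allowed (first limb) |
| Symptoms, 50 mg/dL | Yes, Level 2 | Allowed | Allowed (first limb) |
| No symptoms, 50 mg/dL | Yes, Level 2 | Allowed | Deviation |
| No symptoms, 69 mg/dL | Yes, Level 1 | Allowed | Deviation |

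The first and third rows show the oddity: symptoms without any measurement justify a cut, while a measured 50 mg/dL without symptoms does not.

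**Step 4: participants who never used basal insulin.** The metformin sentence in 6.5.2 is worded for someone whose insulin has been stopped. For a metformin-only participant the wider permission comes from the rationale in 4.2, and 6.5.2 has no metformin step of its own.

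**Step 5: whether anything reconciles the sections.** Nothing found does. All agree that insulin is cut before metformin; they differ only on what counts as hypoglycemia. The SAP's section on hypoglycemic events (4.6.6.1) refers back to Protocol 8.3.3.1. Its Appendix 2 leaves important deviations to a separate Trial Issues Management Plan.

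**Step 6: effect on the analysis.** Rescue therapy in Protocol 6.8.1 and SAP 4.1.8.1 consists of added or increased glucose-lowering treatment. A metformin reduction is neither. The efficacy analysis set drops data only after rescue or after study drug is stopped, so the cut removes nothing. Section 6.8.3 attaches no withdrawal or data exclusion to the deviation.

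**The case against.** The strongest reply is that this is loose drafting. Section 6.8.3 never mentions symptom-free hypoglycemia. Its 54 mg/dL cut-off resembles the glucose-confirmed Level 2 category in 8.3.3.1, so the word that demands symptoms in the second limb may be a slip. That may well be the intent, but a slip that changes who qualifies is still an error in the rule as written.

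Next, a permission in one section and a tighter limit in another can both be obeyed by following the tighter one. That is true. The cost is that the site gives up a step that 6.5.2 offers, and the reader is not told which text governs.

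Third, a reader might infer that several sections independently overrule 6.8.3. They do not. Section 4.2 is rationale and 2.3.1 only refers onward. Only 6.5.2 is an operative dosing instruction, and it is limited to participants off basal insulin. This part of the objection stands.

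Fourth, investigators keep discretion: "it is their responsibility to implement these generally recommended measures, or to modify them". That sentence concerns the 6.5.2 measures and does not lift the deviation rule in 6.8.3. Section 6.8.1 excuses urgent changes from prior consultation, but it speaks of the requirements of its own section, and whether it reaches 6.8.3 is unclear.

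A reader might also infer that the protocol forbids any response to a symptom-free low. It does not: the insulin table in 6.5.2 acts on fasting readings with no symptom condition. Nor are the unspecified events in 8.3.3.1 symptom-free; for them the symptom information is simply missing.

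**Conclusion.** The point holds as a minor error in the text. Section 6.8.3 conflicts with 6.5.2 for participants who have stopped basal insulin, and with the rationale in 4.2 for metformin users generally. The case that matters is a symptom-free value below 54 mg/dL, which 8.3.3.1 itself treats as clinically relevant. Symptom-free values from 54 to below 70 mg/dL also fall in the gap, but there the 54 mg/dL figure in 6.8.3 suggests that a limit was meant, and it is reasonable to keep one.

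The consequence is a deviation entry or a withheld dose reduction in the affected participants. How many there would be cannot be derived: the documents give no rate of symptom-free lows in participants on metformin and off insulin. A reader might infer a bias in the HbA1c comparison or a loss of data; the definitions of rescue and of the analysis sets give no support for lost data, and no effect on the primary result is claimed. The conclusion rests on reading the parenthesis in 6.8.3 literally and its list as closed.

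**What to change.** Amend the protocol as follows.

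- In 6.8.3, replace the parenthesis with: *clinical symptoms of hypoglycemia and/or measured blood glucose <54 mg/dL (3.0 mmol/L), with or without symptoms*. Keep the requirement to stop basal insulin first.
- In 6.5.2 and 4.2, point the metformin step to this 6.8.3 trigger.
- In 6.5.2, state that the step also applies to participants not using basal insulin.

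Replacing the parenthesis with the whole 8.3.3.1 definition would go too far: a symptom-free 69 mg/dL would then justify a metformin cut, and the 54 mg/dL limit would be lost.

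The cost is a few lines of text. Because a dosing rule changes, it should go through an amendment with ethics approval under Appendix 1, not a site memo. No new data are needed and no analysis changes. The small downside is slightly more freedom to alter background metformin.
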